**Figure 3-1 Dose-Escalation Decision Summary**

During 3+3 dose escalation, DLTs will be assessed during the DLT Evaluation Period (Section 3.1.3). If 0 of 3 subjects experience a DLT in a cohort, the next dose level will be opened for enrollment. If  $\geq 2$  of 3 subjects in a cohort experience a DLT, the MTD will have been exceeded and dose escalation will stop. If 1 of 3 subjects in a cohort experiences a DLT, an additional 3 subjects will be treated at that same dose level for a total of 6 subjects. If none of the 3 additional subjects experiences a DLT (1 of 6 subjects with a DLT), dose escalation will continue to the next higher dose level. If 1 or more of the 3 additional subjects experiences a DLT ( $\geq 2$  of 6 subjects with a DLT), the MTD will have been exceeded and dose escalation will not continue. Subjects who do not complete the DLT-evaluation period due to non-DLT reasons will not be considered DLT-evaluable and will be replaced for the DLT evaluation.

The MTD and RP2D will be determined by the Sponsor in consultation with the SMC after a review of all available data. At least 6 subjects must be treated at the putative MTD or RP2D, with no more than 1 incident of DLT.

If 3 or more disease-specific cohorts clear the 0.3 mg/kg or 0.4 mg/kg dose level and the Q6wk schedule, then the SMC may evaluate all the data available to determine an appropriate RP2D and the Part B expansion may proceed for all the cohorts in the study at these dose(s) and schedule.

During dose escalation, additional subjects may be enrolled at a dose level previously declared to be tolerated in order to explore further the safety and tolerability of the regimen. For instance, if

all 3 or 6 subjects necessary for DLT evaluation have been enrolled in a cohort, but have not yet completed the DLT evaluation period, additional subjects may be enrolled at a lower dose level(s), with approval of the Medical Monitor and Sponsor.

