### 3.1.3 Definition of Dose-Limiting Toxicities

The DLT evaluation period is the first 3 weeks of the first cycle of treatment for all subjects in Part A. DLTs are defined as any of the following in the DLT evaluation period, graded according to the National Cancer Institute’s Common Terminology Criteria for Adverse Events (NCI CTCAE), version 4.03:

- Grade 4 thrombocytopenia (or Grade 3 thrombocytopenia with bleeding) lasting more than 7 days and/or requiring platelet transfusion
- Grade 4 neutropenia lasting more than 7 days, and/or requiring hematopoietic growth factor rescue, or any febrile neutropenia (Grade 3 or 4 neutropenia with concurrent fever  $\geq 38.3^{\circ}\text{C}$ )
- Grade 4 anemia unrelated to underlying disease
- Clinically-significant Grade 3 or 4 non-hematologic laboratory abnormality that does not resolve to Grade 0/1 or baseline within 7 days
- Grade 3 or 4 non-laboratory AE with the exception of fatigue, asthenia, nausea, or other manageable constitutional symptom

The following events will not be considered DLTs:

- Any AE  $\geq$  Grade 3 clearly determined to be unrelated to study drug (e.g., PD)
- $\geq$ Grade 3 isolated alkaline phosphatase, amylase or lipase laboratory abnormality of any duration

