#### 8.1.1 Definitions

##### 8.1.1.1 Adverse Events

An AE is defined as any untoward medical occurrence in a patient or clinical investigation subject administered a pharmaceutical product and which does not necessarily have a causal relationship with this treatment. An AE can therefore be any unfavorable and unintended sign (including an abnormal laboratory finding), symptom, or disease temporally associated with the use of a medicinal (investigational) product, whether or not the event is considered causally related to the use of the product.

Such an event can result from use of the drug as stipulated in the protocol or labeling, as well as from accidental or intentional overdose, drug abuse, or drug withdrawal. Any worsening of a pre-existing condition or illness is considered an AE.

Worsening in severity of a reported AE should be reported as a new AE. Laboratory abnormalities and changes in vital signs are considered to be AEs only if they result in discontinuation from the study, necessitate therapeutic medical intervention (including interruption/dose reduction of study drug, starting or discontinuing medication, etc.), meets protocol specific criteria (refer to Sections 5.5 and 8.1 regarding toxicity management) and/or if the Investigator considers them to be AEs.

An elective surgery/procedure scheduled to occur during a study will not be considered an AE if the surgery/procedure is being performed for a pre-existing condition and the surgery/procedure has been pre-planned prior to study entry. However, if the pre-existing condition deteriorates unexpectedly during the study (e.g., surgery performed earlier than planned), then the deterioration of the condition for which the elective surgery/procedure is being done will be considered an AE.

All protocol-related AEs must be collected from the signing of the study specific informed consent until study drug administration.

In addition, AEs with onset or worsening reported by a subject from the time that the first dose of study drug is administered until 70 days have elapsed following discontinuation of study drug administration will be considered as TEAEs.

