### 8.1.2 Adverse Event Severity

The Investigator will rate the severity of each AE according to the NCI CTCAE v4.03. If a reported AE **increases** in severity, the initial AE should be given an outcome date and a new AE reported on a different date from the end date of the previous AE to reflect the change in severity. For all reported SAEs that increase in severity, the supplemental eCRFs also need to be updated to reflect the change in severity.

When CTCAE criteria cannot be used, the event should be graded as defined below:

- Grade 1**        The adverse event is transient and easily tolerated by the subject (mild).
- Grade 2**        The adverse event causes the subject discomfort and interrupts the subject's usual activities (moderate).
- Grade 3/4**      The adverse event causes considerable interference with the subject's usual activities and may be incapacitating or life threatening (severe).
- Grade 5**        The adverse event resulted in death of the subject (severe).

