#### **8.1.4 Deaths**

For SAEs with the outcome of death, the date and cause of death will be recorded on the appropriate case report form.

Deaths that occur during the protocol specified AE reporting period ([Section 8.1.5](#)) that are more likely related to PD will therefore be considered as an expected AE and will not be subject to expedited reporting to regulatory agencies. These SAEs should be reported as "malignant neoplasm progression" and also recorded on the AE eCRF. After the AE reporting period, deaths attributed to PD under study should be recorded only on the end of study (EOS) eCRF.

Death should be considered an outcome and not a distinct event. The event or condition that caused or contributed to the fatal outcome should be recorded as the single medical concept on the AE eCRF. Generally, only one such event should be reported. The term "sudden death" should only be used for the occurrence of an abrupt and unexpected death due to presumed cardiac causes in a patient with or without pre-existing heart disease, within 1 hour of the onset of acute symptoms or, in the case of an unwitnessed death, within 24 hours after the patient was last seen alive and stable. If the cause of death is unknown and cannot be ascertained at the time of reporting, "unexplained death" should be recorded on the AE eCRF. If the cause of death later becomes available (e.g., after autopsy), "unexplained death" should be replaced by the established cause of death.

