## 10.2 Analysis Populations

The following populations will be considered:

- Full Analysis Set: All enrolled subjects who receive any amount of study drug.
- Safety Set: All subjects who receive any amount of study drug and have at least one post-baseline safety evaluation.
- DLT-Evaluable Set: All subjects who receive any amount of study drug and either experienced a DLT or were followed for the full DLT evaluation period.
- Pharmacokinetic-Evaluable Set: All subjects who receive at least 1 dose of study drug and for whom a baseline measurement and at least one blood sample following a dose of study treatment are available.

Based on the actual deviations, the criteria for exclusion of subjects from the different data sets will be specified and updated, if necessary, prior to database lock.

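### The DLT list stops at Grade 4, so a possibly drug-related death in the first 3 weeks with no qualifying Grade 3/4 record is not counted and the subject is replaced

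*Combined protocol and SAP*

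**What the plan says.** Section 3.1.3 sets the DLT window as the first 3 weeks of Cycle 1 in Part A and gives five criteria, any one of which makes a DLT. They cover thrombocytopenia (Grade 4, or Grade 3 with bleeding), neutropenia (Grade 4, or febrile neutropenia at Grade 3 or 4), Grade 4 anemia, Grade 3 or 4 non-hematologic laboratory abnormalities, and a "Grade 3 or 4 non-laboratory AE with the exception of fatigue, asthenia, nausea, or other manageable constitutional symptom".

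Two exclusions follow, and both are open-ended upward. The first removes any AE of at least "Grade 3 clearly determined to be unrelated to study drug (e.g., PD").

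Section 3.1.1 (text with Figure 3-1) gives the replacement rule: "Subjects who do not complete the DLT-evaluation period due to non-DLT reasons will not be considered DLT-evaluable and will be replaced". Section 10.2 defines the DLT-Evaluable Set consistently with this: "All subjects who receive any amount of study drug and either experienced a DLT or were followed for the full DLT evaluation period".

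The AE recording rules decide which deaths leave a Grade 3/4 record. Section 8.1.1.1 says "Worsening in severity of a reported AE should be reported as a new AE", and Section 8.1.2 repeats this and lists Grade 5 (death) apart from Grade 3/4. Section 8.1.4 asks for a fatal outcome to be recorded under a single medical concept: "Generally, only one such event should be reported". It also provides a term for unexplained death, for use "If the cause of death is unknown and cannot be ascertained at the time of reporting".

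**The concern.** The exclusions reach Grade 5 but no inclusion criterion does. A fatal event can be ruled out as a DLT, but nothing rules it in.

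Many fatal courses are still caught. A qualifying Grade 3 or 4 stage before death is its own AE record, and any febrile neutropenia counts. What is left is a death not clearly unrelated to study drug that has no such record:

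- a sudden or unexplained death;
- an event first recorded at Grade 5;
- a death before a duration criterion is met, for example Grade 4 neutropenia that has not yet lasted more than 7 days, with no fever and no growth-factor rescue.

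Followed literally, that subject left the window for a non-DLT reason, is replaced, and drops out of both numerator and denominator of the DLT count. That count drives escalation and the requirement of at most 1 DLT among at least 6 subjects at the putative MTD or RP2D. Clearance of 0.3 or 0.4 mg/kg in three cohorts can also open Part B for all cohorts. The planned DLT incidence summary would omit the death as well, although it would still appear in the Safety Set AE and SAE tables.

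Fatal toxicity is not hypothetical for this drug. Section 1.4 reports 2 related fatal AEs among 104 treated subjects, and Sections 5.5.4 and 5.5.5 mention fatal generalized edema and fatal pneumonitis. Section 3.2.1 justifies a separate escalation per cohort by the limited safety experience outside SCLC.

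**Working it through.** The plan states no operating characteristic for its DLT rule, so there is no figure to reproduce. The check is a reading of the text followed by an illustration.

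**Text.** Taking Sections 3.1.3, 3.1.1 and 10.2 in turn:

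1. A Grade 5 event with no qualifying Grade 3/4 record meets none of the five criteria, so it is not a DLT.
2. The subject did not complete the window, and the reason is not a DLT, so the subject is replaced.
3. The subject had neither a DLT nor full follow-up, so is outside the DLT-Evaluable Set.

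No other section makes a fatal event a DLT.

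**Inputs for the illustration.**

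- The 3+3 rule from Section 3.1.1: escalate on 0/3; expand on 1/3 and escalate if the next 3 are clean; otherwise stop.
- q, the risk of a non-fatal DLT (assumed 10%, 20%, 30%).
- f, the risk of an in-window death lacking a qualifying record (assumed). The documents give no such rate. The only anchor is 2/104 = 1.9% related fatal AEs at any time (Section 1.4).

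**Given one such death and two clean subjects at a level, with no further deaths.**

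- As written, the death is replaced. The replacement is clean (0/3, escalate) with probability 1−q, or has a DLT (1/3, expand, next 3 must be clean): (1−q) + q(1−q)³.
- If the death counts, the level stands at 1/3 and the next 3 must be clean: (1−q)³.

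| q | As written | Death counted |
|---|---|---|
| 10% | 0.9 + 0.1 × 0.729 = 0.973 | 0.729 |
| 20% | 0.8 + 0.2 × 0.512 = 0.902 | 0.512 |
| 30% | 0.7 + 0.3 × 0.343 = 0.803 | 0.343 |

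With two such deaths among the first three subjects, counting them would stop escalation. As written, both are replaced and the level can still clear at 0/3.

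**Averaged over all outcomes at one level.** For a per-subject DLT probability p, the escalation probability is E(p) = (1−p)³ + 3p(1−p)⁵. If the death counts, p = q + f. As written, only evaluable subjects enter, so p = q/(1−f). At q = 20%:

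| f | As written | Death counted | Difference (points) |
|---|---|---|---|
| 0.25% | 0.7075 | 0.7032 | 0.4 |
| 0.5% | 0.7064 | 0.6978 | 0.9 |
| 1% | 0.7042 | 0.6869 | 1.7 |
| 1.9% (2/104) | 0.7001 | 0.6668 | 3.3 |

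At f = 2/104 the difference is 3.0 points for q = 10% and 2.7 points for q = 30%.

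**The case against.** The strongest reply is that this is loose drafting that nobody would apply literally. The exclusion for clearly unrelated AEs extends to Grade 5, which makes sense only if other Grade 5 events were meant to count. A death is an SAE reportable within 24 hours, the SMC can call for more evaluation or cancel a level (Section 3.1), and the MTD/RP2D decision rests on all available data. Section 3.1 also says the escalation process may be described in a separate document, which is not available here. This stands as evidence of intent and of a practical safeguard. It does not repair the rule: the safeguard is discretionary, and it would not restore the subject to the DLT-Evaluable Set.

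The second reply is that the gap is narrow. That is right. Most fatal effusions, for instance, would pass through a Grade 4 stage, and the one-event guidance in Section 8.1.4 does not cancel earlier-grade records. The duration example is also arguable for the non-hematologic laboratory criterion, since an abnormality present at death never resolved. It does hold for the hematologic criteria that require more than 7 days, unless transfusion or growth-factor rescue has already triggered them.

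The third reply is that the numbers depend on assumptions. The 0.90 versus 0.51 contrast conditions on a rare event and on mechanical use of the rule. The 1.9% overstates f: it covers all follow-up, includes doses up to 0.8 mg/kg every 3 weeks against this trial's maximum of 0.4 mg/kg every 6 weeks, and neither death is shown to have lacked a Grade 3/4 stage. It should be read only as a high-end value. The harm is also bounded, with three dose levels and so at most two escalations per cohort.

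**Conclusion.** The concern holds. Followed as written, Sections 3.1.3, 3.1.1 and 10.2 together score a possibly related early death without a qualifying Grade 3/4 record as no DLT, and replace the subject. Counting such deaths was probably intended, but no criterion says so.

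The conclusion itself rests on the text. Its size rests on assumed values of q and f and on the rule being applied without SMC intervention. When such a death occurs alongside two clean subjects, the escalation probability is inflated by 0.973 − 0.729 = 0.24 (q = 10%), 0.902 − 0.512 = 0.39 (q = 20%) or 0.803 − 0.343 = 0.46 (q = 30%). Averaged over all cases the inflation at q = 20% is 0.4 to 3.3 points per level for f between 0.25% and 1.9%. This should be fixed: the average effect is small, but the rule fails in the one situation where a dose-escalation rule most needs to be right.

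**What to change.** In Section 3.1.3, change the non-laboratory criterion to Grade 3 or higher, and add to the DLT list any death in the window that is not clearly unrelated to study drug. The second change is needed as well, because an unexplained death, or one occurring before a hematologic duration criterion is met, should count without debate over how the AE was termed. In Sections 3.1.1 and 10.2, state that these subjects are DLT-evaluable and are not replaced.

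The cost is a wording change in three sections, with no new procedures or data. Extra subjects are needed only if such a death occurs and the level has to expand to 6. If any such death has already occurred in Part A, the DLT summary should be produced under the corrected definition.

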### 3.1.4 Retreatment

Retreatment with rovalpituzumab tesirine may be permitted, with Medical Monitor and Sponsor approval, for subjects who tolerate all doses of rovalpituzumab tesirine, achieve clinical benefit

as defined by stable disease or better, receive no other systemic anti-cancer therapy after rovalpituzumab tesirine as administered in accordance with this protocol, and then experience PD at least 12 weeks after the most recent dose of rovalpituzumab tesirine. The retreatment dose level and regimen for each subject will be determined by the Medical Monitor, Sponsor or designee and the site Investigator, not to exceed the MTD.

### **3.2 Discussion and Rationale for Study Design**

#### **3.2.1 Study Design**

This is the first clinical study with rovalpituzumab tesirine that will have cohorts dedicated to specific tumor types other than SCLC. Since the safety and tolerability of rovalpituzumab tesirine in tumor types other than SCLC has not been well-studied, separate dose escalations are planned for each cohort. In addition, some NEC cancer types warrant specific considerations in trial design, such as the utility of bone scintigraphy and PSA in prostate cancer (Kulke 2011; Scher 2016), and the safety and tolerability of rovalpituzumab tesirine may differ in cancers of different primary organs (Stemcentrx data on file). Therefore, some specific NECs will be enrolled and analyzed in distinct cohorts in this study, including LCNEC, NEPC, and high-grade GEP NEC (Section 3.1; Appendix 13.7).

Each Part A dose escalation will utilize a traditional rule-based design, including 3+3 cohorts at anticipated active doses to evaluate the safety and tolerability of multiple dose levels in a disease-specific fashion (Le Tourneau 2009), and will allow definition of the MTD, if one can be identified. In Part B, potential therapeutic doses (i.e., the MTD and/or lower doses as guided by the cumulative clinical experience in Part A) may be studied in expansion cohorts of subjects with specific solid tumor types.

Evaluation of the study endpoints will inform the safety profile of rovalpituzumab tesirine in advanced solid tumors and may provide evidence of antitumor activity that could influence the trial design of subsequent studies.

#### **3.2.2 Method of Assigning Subjects to Treatment Groups**

Upon approval of subject registration, the Sponsor or designee will assign each subject to a disease-specific cohort. The cohort assignment decisions will be documented in the clinical trial master file.

#### **3.2.3 Rationale for Selection of Doses**

In a Phase 1 study with rovalpituzumab tesirine, the MTD was established at 0.4 mg/kg Q3wk based on the incidence of Cycle 1 toxicities, while the RP2D in SCLC was chosen as 0.3 mg/kg Q6wk based on the toxicity and efficacy profile during multiple cycle dosing (Stemcentrx data on file). For this study, dosing will begin with 0.2 mg/kg Q6wk, a dose level -1 relative to the

RP2D (that was determined for SCLC), and dose escalation is planned to continue through 0.4 mg/kg Q6wk, the MTD in SCLC.

### **3.2.4 Blinding**

This is not a blinded trial.

## 4. Study Population

Subjects must meet all of the enrollment criteria to be eligible for this study. Eligibility criteria may not be waived by the Investigator and are subject to review in the event of Good Clinical Practice (GCP) audit and/or appropriate health regulatory authority inspection.

To be eligible for retreatment as described in [Section 3.1.4](#), subjects must meet all inclusion and exclusion criteria outlined in this section.

### 4.1 Inclusion Criteria

1. Ability to provide written informed consent.
2. Histologically confirmed, unresectable advanced solid malignancy other than SCLC.  
*Note:* Subjects with prostate cancer must also meet the additional prostate-specific criteria in [Appendix 13.7](#).
3. Measurable disease, defined as at least one tumor lesion  $\geq 10$  mm in the longest diameter, or a lymph node  $\geq 15$  mm in short-axis measurement, assessed by computerized tomography (CT) scan (by RECIST v1.1).
4. Disease refractory to standard therapy or for which standard or curative therapy does not exist or is not considered appropriate by the Investigator.
5. DLL3-expressing malignancy based on central immunohistochemical (IHC) testing of representative baseline tumor tissue (archived tissue or on-study biopsy). Positive is defined as staining in  $\geq 1\%$  of tumor cells.
6. Eastern Cooperative Oncology Group (ECOG) performance status of 0 or 1. Refer to [Appendix 13.3](#) for conversion of performance status using Karnofsky scales, if applicable.
7. Minimum life expectancy of at least 12 weeks.
8. Subjects with a history of central nervous system (CNS) metastases must have documentation of stable or improved brain imaging for at least 2 weeks after completion of definitive treatment and within 2 weeks prior to first dose of Study Drug, off or on a stable dose of corticosteroids. Definitive treatment may include surgical resection, whole brain irradiation, and/or stereotactic radiation therapy. (Applicable to tumor types of non-CNS primary origin only).
9. Recovery to Grade 1 of any clinically significant toxicity (excluding alopecia) prior to initiation of study drug administration.
10. Satisfactory laboratory parameters:
  - a. Absolute neutrophil count (ANC)  $\geq 1,500/\mu\text{L}$ .
  - b. Platelet count  $\geq 75,000/\mu\text{L}$ .
  - c. Hemoglobin  $\geq 8.0$  g/dL.
  - d. Total bilirubin  $\leq 1.5 \times$  upper limit of normal (ULN) or  $\leq 3 \times$  ULN for subjects with Gilbert's disease.

- e. Alanine aminotransferase (ALT) and aspartate aminotransferase (AST)  $\leq 2.5 \times$  ULN ( $\leq 5 \times$  ULN if evidence of hepatic involvement by malignant disease).
  - f. Creatinine  $\leq 1.5 \times$  ULN or estimated glomerular filtration rate (eGFR)  $\geq 30$  mL/min/1.73m^2.
  - g. Serum albumin  $\geq 3.0$  g/dL
11. Last dose of any prior therapy administered by the following time intervals before the first dose of study drug:
- a. Chemotherapy, small molecule inhibitors, radiation, and/or other investigational anticancer agents (excluding investigational monoclonal antibodies): 2 weeks.
  - b. Immune-checkpoint inhibitors (e.g., anti-PD-1, anti-PD-L1, or anti-CTLA-4), monoclonal antibodies, antibody-drug conjugates, radioimmunoconjugates, or T-cell or other cell-based therapies: 4 weeks (2 weeks with documented disease progression).
12. If female, subject must be either postmenopausal defined as:
- Age  $>55$  years with no menses for 12 or more months without an alternative medical cause.
  - Age  $\leq 55$  years with no menses for 12 or more months without an alternative medical cause AND follicle stimulating hormone (FSH) level  $>40$  IU/L.  
OR
  - Permanently surgical sterile (bilateral oophorectomy, bilateral salpingectomy, or hysterectomy)  
OR
  - A Woman of Childbearing Potential (WOCBP) practicing at least one protocol specified method of birth control ([Section 4.3.1](#)) starting at Study Day 1 through at least 6 months after the last dose of study drug.
13. If the male subject is sexually active, he must agree, from Study Day 1 through at least 6 months after the last dose of study drug, to practice the protocol specified contraception ([Section 4.3.2](#)).
14. Females of childbearing potential must have a negative serum pregnancy test result at screening and a pre-dose negative urine pregnancy test on Cycle 1 Day 1 (C1D1). Females of non-childbearing potential (either postmenopausal or permanently surgically sterile as defined in [Section 4.3](#)) at screening do not require pregnancy testing.

